3.3.2 Demographics and Baseline Characteristics

Demographic information related to sex, age, race, weight, height, and body mass index (BMI) will be presented by treatment group and for all subjects combined. A summary of baseline characteristics may include, but not be limited to medical history and cardiovascular disease history.

3.3.3 Study Drug Exposure

The number of subjects who received investigational product at Days 1, 8, and 15 for Cohorts 1-3 and at Days 1, 3, and 10 for Cohort 4 will be summarized descriptively by the amount of the product received (i.e., entire dose vs entire dose not administered) and the reasons subject did not receive entire dose (i.e., AEs vs other) will also be summarized descriptively.

3.3.4 Concomitant Medications

Concomitant medications will be coded using the latest available version of AstraZeneca Drug Dictionary and summarized by preferred term with frequency and percentage by treatment group. In addition, concomitant medications will summarized by Anatomical Therapeutic Chemical (ATC) Classification System.

3.4 Pharmacodynamic Endpoint(s) and Analyses

3.4.1 Pharmacodynamic Endpoint(s)

The PD parameters of primary interest are the baseline-adjusted HDL-C, HDL-CE, and CE AUC_{0-96hr} following Dose 3 administration (AUC_{0-96hr Dose 3}).

Other endpoints including AUC_{0-96hr Dose 1}, AUC_{0-96hr Dose 3}, AUC_{0-168hr Dose 1}, AUC_{0-168hr Dose 3}, and AUC_{1-22d} (AUC from time 0 on Day 1 through 168 hours after Dose 3) for HDL-C, TC, FC, CE, HDL-CE, HDL-UC, non-HDL-C, non-HDL-CE, non-HDL-UC, LDL-C (by direct measure), TG, VLDL-C, apoA1 and apoB.

For Cohorts 1-3, pre β 1-HDL will be reported at baseline, 12 hours post dose 1, day 2, prior to dose 3 and 12 hours post dose 3, days 16, 19, and 22. ApoAII, apoCIII, and apoE will be reported at baseline, day 19, and day 22.

For Cohorts 4, $pre\beta1$ -HDL will be reported at baseline, 12 hours post dose 1, day 2, day 5, prior to dose 3 and 12 hours post dose 3, days 11, 14, and 17. ApoAII, apoCIII, and apoE will be reported at baseline, day 14, and day 17.

3.4.2 Analysis of Pharmacodynamic Endpoint(s)

AUC will be calculated using the trapezoidal rule. Statistical comparison with regard to AUC between treatment groups will be conducted using analysis of covariance (ANCOVA) by adjusting baseline values and treatment group comparing each active treatment against placebo. The dose-response profile with regard to HDL-C may be explored using MCP-MOD procedure.

Change and the percent change from baseline at each time point for serum concentration of HDL-C, TC, FC, CE, HDL-CE, HDL-UC, non-HDL-C, non-HDL-CE, non-HDL-UC, LDL-C (by direct measure), TG, VLDL-C, apoA1, pre β 1-HDL, apoAII, apoCIII, apoE, and apoB will be analyzed and compared using ANCOVA by adjusting baseline values and treatment. Descriptive statistics will be provided by treatment group for maximum response (R_{max}) and time to maximum response [(R)T_{max}].

For ANCOVA, if the data is not normally distributed, the analyses will be conducted on rank-transformed data.

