This is a Phase 2a randomized, blinded (subject/investigator blinded, MedImmune unblinded), placebo-controlled, dose-escalation study to evaluate the safety, PK/PD, and immunogenicity of repeat doses of MEDI6012 in adult subjects with stable atherosclerotic CVD. At least 32 subjects are planned to be randomized across approximately 10 study sites in the United States of America (USA) to evaluate 4 dose levels (40, 120, 300 mg, and an IV push dosing regimen that includes a loading dose of 300 mg followed by a 150 mg maintenance dose at 48 hours and a 100 mg maintenance dose 7 days later) of MEDI6012. Subjects in Cohorts 1-3 will be administered investigational product weekly via intravenous (IV) infusions. Cohort 4 subjects will be administered investigational product using a loading dose of 300 mg (Dose 1) of MEDI6012, a second dose of 150 mg at 48 hours followed by a maintenance dose of 100 mg 1 week later with all doses given by IV push. For each cohort, 8 subjects are planned for randomization in a 6:2 ratio to receive MEDI6012 or placebo. Investigational product will be administered as a 1-hour IV infusion (Cohorts 1-3) or an IV push (Cohort 4).

Subjects will undergo a screening period of up to 28 days. For subjects requiring a washout of dyslipidemia medication or supplement, a 56 day screening period is allowed. Subjects will be admitted to the study center the evening prior to randomization and first dose administration (Day -1) and prior to third dose administration and remain at the study center for 24-36 hours. In lieu of overnight admission, outpatient arrangements such as a hotel stay near the study center or return to home may alternatively be provided. For dose 2, subjects will be observed as inpatients for at least 8 hours following dosing. For Cohort 4, outpatient arrangements may be provided through Day 4. Subjects will be followed as outpatients through 56 days after the last dose of investigational product (Day 71 visit for Cohorts 1-3, Day 66 visit for Cohort 4). Subjects will be encouraged to maintain a healthy lifestyle, including diet and exercise, during the study period.

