3 STUDY DESIGN

3.1 Description of the Study

3.1.1 Overview

This is a Phase 2a randomized, blinded (subject/investigator blinded, MedImmune unblinded), placebo-controlled, dose-escalation study to evaluate the PK/PD, safety and immunogenicity of repeat doses of MEDI6012 in adult subjects with stable atherosclerotic CVD. At least 32 subjects are planned to be randomized across approximately 10 study sites in the United States of America (USA) to evaluate 4 dose levels (40, 120, 300 mg, and a IV push dosing regimen that includes a loading dose of 300 mg followed by a 150 mg

maintenance dose at 48 hours and a 100 mg maintenance dose 7 days later) of MEDI6012. Subjects in Cohorts 1-3 will be administered investigational product weekly via intravenous (IV) infusions. Cohort 4 subjects will be administered investigational product using a loading dose of 300 mg (Dose 1) of MEDI6012, a second dose of 150 mg at 48 hours, followed by a maintenance dose of 100 mg 1 week later. For each cohort, 8 subjects are planned for randomization in a 6:2 ratio to receive MEDI6012 or placebo. Investigational product will be administered as a 1-hour IV infusion (Cohorts 1-3) or IV push (Cohort 4).

Subjects will undergo a screening period of up to 28 days. For subjects requiring a washout of dyslipidemia medication or supplement, a 56-day screening period is allowed. For Cohorts 1-3, subjects may be admitted to the study center the evening prior to randomization and first dose administration (Day -1) and prior to third dose administration (Day 15) and remain at the study center for 24-36 hours. In lieu of overnight admission, outpatient arrangements such as a hotel stay near the study center or a return to home may alternatively be provided. For Dose 2 (Day 8), subjects will be observed as inpatients for at least 8 hours following dosing. Subjects will be followed through 56 days after the third dose of investigational product (Day 71).

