4.8.6 Pharmacodynamics

The PD parameters of primary interest are the baseline-adjusted HDL-C, HDL-CE, and CE AUC_{0-96hr} following Dose 3 administration (AUC_{0-96hr Dose 3}). AUC will be calculated using the trapezoidal rule. Statistical comparison between treatment groups with placebo group combined will be conducted using analysis of covariance (ANCOVA) by adjusting baseline HDL-C and treatment group. The dose-response profile with regard to HDL-C may be explored using MCP-MOD procedure. Other endpoints including AUC_{0-96hr Dose 1}, AUC_{0-168h Dose 3}, and AUC_{1-22d} (AUC from time 0 on Day 1 through 168 hours after Dose 3) for HDL-C, TC, FC, CE, HDL-CE, HDL-UC, non-HDL-C, non-HDL-CE,

non-HDL-UC, LDL-C (by direct measure), apoA1 and apoB will be analyzed similarly to the primary PD endpoint.

Change and the percent change from baseline at each time point for each of the above lipids, lipoproteins, and apolipoproteins as well as VLDL-C, TG, pre\(\beta\)1-HDL, apoAI, apoAII, apoCIII, and apoE will be analyzed and compared using ANCOVA by adjusting baseline and treatment group with placebo group combined.

For ANCOVA, if the data is not normally distributed, the analyses will be conducted on rank-transformed data.

Descriptive statistics will be provided by treatment group for R_{max} (maximum biomarker response) and $(R)T_{max}$ (time to reach maximum biomarker response) for each of these as well. Details of these analyses will be specified in the SAP.

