2 STUDY OVERVIEW

2.1 Study Objectives

2.1.1 Primary Study Objective(s)

1. The primary safety objective is to evaluate the safety of MEDI6012 following repeat dosing in subjects with stable atherosclerotic cardiovascular disease (CVD) over time to Day 71 (Cohorts 1-3) or Day 66 (Cohort 4).

Primary Safety Endpoints: Safety and tolerability of MEDI6012 as measured by the incidence of treatment-emergent adverse events (TEAEs) and treatment-emergent serious adverse events (TESAEs) and clinically important changes in 12 lead electrocardiogram, vital signs, and clinical laboratory evaluations over time to Day 71 (Cohorts 1-3) or Day 66 (Cohort 4).

2. The primary PD objective is to establish that repeat dosing with MEDI6012 results in a sustainable and reversible dose-dependent response for HDL-C, HDL-CE, and CE.

Primary PD Endpoint: Baseline adjusted area under the concentration-time curve from time 0 to 96 hours post dose 3 (AUC_{0-96hr}) for HDL-C, HDL-CE, and CE.

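### The primary PD objective is a dose-dependent response in three markers, but the only committed test compares each regimen with placebo; dose-response analysis is optional and covers HDL-C alone

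*SAP*

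**What the plan says.** SAP 2.1.1 states the primary PD objective as establishing that repeat dosing "results in a sustainable and reversible dose-dependent response for HDL-C, HDL-CE, and CE". Protocol 2.1.1 says the same, and the second primary hypothesis in Protocol 1.6.1 also claims a dose-dependent response in these markers. The endpoint is the baseline-adjusted AUC0-96hr after Dose 3 (SAP 3.4.1): "The PD parameters of primary interest are the baseline-adjusted HDL-C, HDL-CE, and CE".

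SAP 3.4.2 analyses AUC by ANCOVA with baseline and treatment group in the model, "comparing each active treatment against placebo". Protocol 4.8.6 describes an ANCOVA between treatment groups with the placebo groups combined. It names no contrasts, and Protocol 4.8.1 leaves endpoint analysis details to the SAP. On dose-response both documents offer one sentence: "The dose-response profile with regard to HDL-C may be explored using MCP-MOD procedure". It gives no candidate models, dose coding or set of cohorts, and does not mention HDL-CE or CE.

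The documents also count dose levels differently. Protocol 3.1.1 says the study is "to evaluate 4 dose levels (40, 120, 300 mg, and a IV push dosing regimen", so Cohort 4 is the fourth level; the synopsis agrees. Protocol 3.1.2 counts three infusion levels and lists Cohort 4 apart. SAP 2.2 says three but then lists four entries, including the IV push regimen.

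**The concern.** A significant difference from placebo shows that a regimen does something. It does not show that more drug does more. If the response were the same at 40, 120 and 300 mg, each placebo comparison could be significant and the committed analysis would look just as it does under a dose-response. Conversely, a steep dose-response with a weak 40 mg arm could miss on that arm and look less convincing than a plateau.

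What is at stake is whether the primary PD objective has a committed analysis at all. As written, the team would have to rely on an optional exploration of HDL-C or on looking across point estimates, and HDL-CE and CE would have nothing. Whether Cohort 4 belongs on the dose axis is also left open, to be decided after data are available to an unblinded sponsor team (Protocol 4.6.2).

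**Working it through.** **Plan's own figure.** The sample-size text is not visible in the public documents (Protocol 4.8.2, SAP 2.4), so there is no stated power to reproduce. That is not held against the plan.

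**Inputs from the documents.**
- 6 active and 2 placebo subjects per cohort: 6 per dose, and 4 × 2 = 8 pooled placebo.
- Predicted baseline-adjusted HDL-C AUC over 336–432 hours (Protocol Table 3.2.1-1): 1,520, 3,440 and 5,600 mg*hr/dL for 40, 120 and 300 mg. Dose 3 on Day 15 is 14 × 24 = 336 hours and 336 + 96 = 432, so this is the primary window.

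**Assumptions.** Two-sided 5%, normal data, placebo mean 0, and a common SD from 800 to 2,500 mg*hr/dL. Simple contrasts stand in for the ANCOVA. Variance is pooled over placebo and the three infusion groups: 26 − 4 = 22 degrees of freedom.

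**Dose versus placebo.** t = difference / [SD × √(1/8 + 1/6)] = difference / (0.540 × SD). At SD 1,200 the expected t is 1,520/648 = 2.35 for 40 mg (power 0.61), 5.31 for 120 mg and 8.64 for 300 mg (power about 1.00 each). The 40 mg arm limits the chance that all three are significant.

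**Log-dose slope among active doses.** The logs of 40, 120 and 300 are 3.689, 4.787 and 5.704, with mean 4.727. The centred coefficients are −1.038, 0.061 and 0.977, with sum of squares 2.035. At the predicted means the contrast is −1.038 × 1,520 + 0.061 × 3,440 + 0.977 × 5,600 ≈ 4,103 (unrounded coefficients). Its standard error is SD × √(2.035/6) = 0.582 × SD. At SD 2,500 the expected t is 4,103/1,456 = 2.82.

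**Results** (simulated; at least 20,000 trials per cell)

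| Assumed SD | Flat 3,440: all three placebo tests significant | Predicted means: all three significant | Flat: positive slope | Predicted means: slope power |
|---|---|---|---|---|
| 800 | 100% | 92% | about 2.5% | 1.00 |
| 1,200 | 99.7% | 61% | about 2.5% | 1.00 |
| 1,600 | 92% | 39% | about 2.5% | 0.99 |
| 2,000 | 70% | 26% | about 2.5% | 0.92 |
| 2,500 | 44% | 17% | about 2.5% | 0.77 |

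If the variance comes from the 18 infusion-treated active subjects alone (15 degrees of freedom), slope power is 0.91 at SD 2,000 and 0.75 at SD 2,500.

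**Unequal variance check.** With placebo SD 250 and active SD equal to 30% or 50% of each mean, the flat case gives all three significant in 100% or 98% of trials. The predicted means give 92% or about 33%. Slope power is 1.00 or about 0.92.

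**Cohort 4 on the dose axis.** The regimen could be coded as 300 mg (first dose), 100 mg (third dose) or 300 + 150 + 100 = 550 mg (total, against 120, 360 and 900 mg in Cohorts 1–3). These codings place it differently relative to the infusion cohorts, and neither document chooses one.

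**The case against.** The best reply is that a plateau is a logical illustration and not the expected outcome: the single-dose study showed dose-dependent increases in HDL-C, HDL-CE and CE (Protocol 1.5 and 3.2.1). The ANCOVA would also give adjusted effects at 40, 120 and 300 mg against one pooled placebo group, so a plateau would be visible in the estimates. Both points are fair. They narrow the gap to the lack of a committed trend analysis. They do not close it, because the objective is to establish dose-dependence under repeat dosing and no planned result would do so.

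A second reply is that the percentages depend on SDs that nobody can see. That also stands, and it is why a range is shown. It would be wrong, for example, to say that the slope test has over 99% power; that holds only at the lower SDs.

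A reader might go further and infer that Cohort 4 will bend the MCP-Mod curve. No section puts Cohort 4 in that analysis, Protocol 3.1.2 lists it apart, and it has its own secondary objective. A figure for the distortion would need an invented dose coding and predicted peaks, since the documents give no predicted Cohort 4 AUC. A reader might also infer that MCP-Mod drives dose selection. The documents tie dose selection to PK/PD modelling and dose-exposure-response work (Protocol 3.2.1, 3.2.2, 3.2.4.3), not to MCP-Mod.

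Finally, three markers by four regimens makes 12 placebo comparisons with no visible order. An error rule could have stood in the text that is not visible, and fixed-order testing with six subjects per regimen in Phase 2a is a trade-off, so it is not pressed here.

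**Conclusion.** The point holds in this form: the primary PD objective claims dose-dependence for three markers, and the committed analysis cannot tell dose-dependence from a plateau for any of them. That conclusion follows from the text and needs no assumed SD.

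The size is illustrative. It rests on the protocol's predicted HDL-C means, a two-sided 5% level, 8 placebo and 6 subjects per dose, and an assumed SD. At every SD tried, a flat response passes all three placebo tests more often than the predicted dose-response does. The slope test keeps its error rate in the flat case and has useful power with the planned subjects, falling to about 0.75 at the top of the range. No such figures can be given for HDL-CE or CE, because the documents show no predicted AUC for them.

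For Cohort 4, the documents support only two statements: its place in any dose-response analysis is unspecified, and the counts of dose levels disagree.

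**What to change.** In SAP 3.4.2, replace the optional sentence with one pre-specified trend analysis of baseline-adjusted AUC0-96hr Dose 3 across the 40, 120 and 300 mg weekly infusion cohorts. A log-dose slope or a linear contrast among the active doses would serve; name one. Apply it to HDL-C, HDL-CE and CE with the same baseline adjustment as the ANCOVA. MCP-Mod, with pooled placebo as the zero dose and its candidate models listed, can be supportive. Keep the placebo comparisons as estimates with confidence intervals.

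State that Cohort 4 is left out of the trend analysis and MCP-Mod and is reported as a separate regimen against pooled placebo. Exposure-response modelling is not affected. Reconcile the number of dose levels across the protocol synopsis, Protocol 3.1.1 and 3.1.2, and SAP 2.2.

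The cost is a few lines of SAP text and some programming, with no extra subjects or samples. The sponsor should accept that the slope test may be inconclusive if the SD is near the top of the range. A fixed testing order over the three markers is optional; it would make the HDL-CE and CE claims conditional on HDL-C.

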3.5 Safety Analyses

The primary safety endpoints are the safety and tolerability of MEDI6012 following repeatweekly dosing as measured by the incidence of TEAEs and TESAEs, and clinically important changes in 12-lead ECG, vital signs, and clinical laboratory evaluations over time to Day 71 (Cohorts 1-3) or Day 66 (Cohort 4).

The evaluations will be descriptive in nature, and observed differences will be evaluated for medical relevance. No formal statistical comparisons will be performed for the safety summaries.

3.5.1 Adverse Events and Serious Adverse Events

AE collection begins after the subject signs the informed consent document and lasts until the end of the study. TEAEs and TESAEs will be coded by the most updated version of the Medical Dictionary for Regulatory Activities (MedDRA), and the type, incidence, severity and relationship to investigational product will be summarized. Specific AEs will be counted once for each subject for calculating percentages. In addition, if the same AE occurs multiple times within a particular subject, the highest severity and level of relationship observed will be reported. All TEAEs and TESAEs will be summarized overall, as well as categorized by MedDRA system organ class and preferred term and by severity and relationship to investigational product.

Infusion site reactions for local reactions will be checked. Infusion site related AEs will be summarized.

3.5.2 Adverse Events of Special Interest

An adverse event of special interest (AESI) is one of scientific and medical interest specific to understanding of the investigational product and may require close monitoring and rapid communication by the investigator to the sponsor. An AESI, which is defined in Sections 5.3 and 5.6.2 of the protocol as hepatic function abnormality meeting the definition of Hy's law, may be serious or non-serious. Treatment-emergent AESIs will be summarized together with other AEs/SAEs. No separate summary tables will be produced.

3.5.3 Deaths and Treatment Discontinuations due to Adverse Events

Number of subjects who died or discontinued from the treatment due to AEs will be summarized by treatment group.

3.5.4 Clinical Laboratory Evaluation

Clinical laboratory safety tests including serum chemistry, hematology, urinalysis, and others will be summarized using descriptive statistics at each time point by treatment group. Change from baseline to each post baseline time point and shift from baseline relative to normal range will also be summarized, where appropriate.

3.5.5 Other Safety Evaluations

3.5.5.1 Vital Signs

Vital sign (blood pressure, respiratory rate, pulse, pulse oximetry, and body temperature) results and change from baseline will be summarized using descriptive statistics at each time point by treatment group.

3.5.5.2 Electrocardiogram

ECG parameters as well as change from baseline for quantitative measurements (RR, PR, QRS, QT, QTcF, QTcB, and heart rate) will be assessed and summarized descriptively by treatment group at each time point.

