- Fulfill Hy's law defined as "An increase in aspartate transaminase (AST) or alanine transaminase (ALT) \geq 3 × upper limit of normal (ULN) and total bilirubin (TBL) \geq 2 × ULN, where no other reason can be found to explain combination of increases

*Note: A difference of \geq 30% is deemed to be biologically relevant because intrasubject variability for HDL-C is estimated at 2% to 5% (when factors such as diet and exercise are controlled) and HDL-C assay variability ranges from 12% to 20%. A potential mechanism for a decreased HDL-C response is the development of a nAb response against MEDI6012 that also affects endogenous LCAT activity. For this reason, in the setting of a \geq 30% decrease in HDL or ADA titer \geq 8, the dose-escalation decision will be delayed to allow for collection and review of additional data including PK and ADA/nAb as well as safety and PD data.

Dose escalation will be paused if, within the given cohort, the DEC review determines that ≥ 2 subjects who received MEDI6012 have any of the following:

- An average absolute (regardless of baseline value) QTcF > 500 ms, or an increase of QTcF > 60 ms above baseline confirmed (persistent for ≥ 5 minutes) on a repeat 12-lead ECG
- Tachycardia in a subject receiving MEDI6012, defined as resting supine pulse rate > 125 bpm persisting for at least 10 minutes

- Hypertension in a subject receiving MEDI6012, defined as an increase in resting supine systolic blood pressure (BP) > 40 mm Hg to above 180 mm Hg and persisting for at least 10 minutes
- Symptomatic bradycardia, with a simultaneous resting supine pulse rate < 45 bpm while awake, persisting for at least 10 minutes; or asymptomatic bradycardia defined as resting supine pulse rate < 30 bpm while awake persisting for at least 10 minutes
- Other clinically significant changes in laboratory values or safety parameters

If any of these safety criteria are met, the data will be reviewed by a MedImmune safety review board to determine whether to continue the study and/or escalate the dose. If dose-escalation stopping criteria are not met but a potential safety signal (not considered severe) indicates that further dose escalation may affect subject safety, the cohort may be expanded at the current dose level or an intermediate or lower dose level may be evaluated. Similarly, if there is a desire for efficacy signal verification, the cohort may be expanded or a cohort added.

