2.4 Sample Size

3 STATISTICAL METHODS

3.1 General Considerations

Data will be provided in listings sorted by cohort, treatment group and subject number. Tabular summaries will be presented by cohort and treatment group with placebo group combined when appropriate. Categorical data will be summarized by the number and percentage of subjects in each category. Continuous variables will be summarized by descriptive statistics, including mean, standard deviation, median, minimum, and maximum. Baseline values will be defined as the last valid assessment prior to the first administration of investigational product.

Data analyses will be conducted using the SAS[®] System Version 9.3 or higher (SAS Institute Inc., Cary, NC) unless otherwise specified. All analysis outputs will be validated according to MedImmune SAS programming standards and MedImmune validation procedures.

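### The SAP specifies no subject-level count for the ECG and vital-sign part of the primary safety endpoint; its group summaries by time point cannot show how many different subjects had a marked change

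*SAP*

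**What the plan says.** SAP 2.1.1 and protocol 2.2.1 give the primary safety endpoint as the incidence of TEAEs and TESAEs together with "clinically important changes in 12 lead electrocardiogram, vital signs, and clinical laboratory evaluations", followed to Day 71 (Cohorts 1-3) or Day 66 (Cohort 4).

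The planned analyses of the second component are:

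- **Safety in general (SAP 3.5):** "The evaluations will be descriptive in nature, and observed differences will be evaluated for medical relevance". No criterion for relevance is given.
- **Vital signs (SAP 3.5.5.1):** "results and change from baseline will be summarized using descriptive statistics at each time point by treatment group".
- **ECG (SAP 3.5.5.2):** parameters and changes from baseline "will be assessed and summarized descriptively by treatment group at each time point".
- **Laboratory tests (SAP 3.5.4):** descriptive statistics, and in addition "shift from baseline relative to normal range will also be summarized, where appropriate".

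SAP 3.1 defines the descriptive statistics for continuous variables as "including mean, standard deviation, median, minimum, and maximum". It also provides numbers and percentages for categorical data, but the SAP defines no ECG or vital-sign category to which that rule could apply. Protocol 4.8.3.3 and 4.8.3.4 go no further, except for an exposure-response ECG analysis that will not be in the CSR.

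Protocol 3.1.3 does contain numeric limits at subject level, for example "an increase of QTcF > 60 ms above baseline confirmed". They serve decisions to pause dose escalation, which are triggered when at least two MEDI6012 subjects in a cohort are affected.

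**The concern.** A clinically important change happens to a subject. The natural summary is how many subjects in each group had one during follow-up. The SAP instead describes the distribution of values in each group, one time point at a time.

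With 6 active subjects per cohort, a group mean moves little when one subject changes markedly. The maximum at a time point shows only that at least one subject reached that value there. Neither statistic links subjects across visits, so the tables cannot separate one subject affected repeatedly from several subjects affected once each. That matters here because protocol 3.1.3 itself treats the step from one to two affected subjects as meaningful for these measures. Two of the three measurement domains in this part of the primary safety endpoint thus reach the report without a tabulated count, whereas laboratory data at least have a shift summary.

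**Working it through.** The public documents state no figure to reproduce on this point, so the check compares the texts and then tests whether the planned statistics can yield a count.

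**Step 1: endpoint against analysis.**

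| Domain named in the endpoint | Group statistics by time point | Categorical or shift summary | Any-visit count of subjects |
|---|---|---|---|
| Laboratory (SAP 3.5.4) | yes | yes, shift against normal range | none stated |
| Vital signs (SAP 3.5.5.1) | yes | none stated | none stated |
| ECG (SAP 3.5.5.2) | yes | none stated | none stated |

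**Step 2: can the planned statistics give the count?** The inputs are:

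- Group size: 6 active and 2 placebo per cohort (SAP 2.2). Four cohorts give 4 × 6 = 24 active and 4 × 2 = 8 placebo.
- Statistics: mean, SD, median, minimum and maximum (SAP 3.1).
- Assumed QTcF changes at two post-baseline visits: +65 ms where a subject is affected and 0 otherwise. These values are illustrative.

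Case A has the same subject at +65 ms at both visits. Case B has one subject at +65 ms at the first visit and a different subject at +65 ms at the second. In both cases each visit holds one value of 65 and five of 0:

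- Mean = 65/6 = 10.83 ms
- SD = √{[(65 − 10.83)² + 5 × (0 − 10.83)²]/5} = 26.54 ms
- Median 0, minimum 0, maximum 65 ms

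The two visit rows are therefore identical in A and B. The number of subjects above 60 ms at any visit is 1 of 6 (16.7%) in A and 2 of 6 (33.3%) in B. The planned statistics do not determine the count.

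**Step 3: sensitivity of the mean.** One subject of six at +60 ms, the others at 0, moves the group mean by 60/6 = 10 ms. Two such subjects at the same visit move it by 120/6 = 20 ms.

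**Step 4: can the limits in protocol 3.1.3 be applied to scheduled readings?** Only their numeric part can.

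- The QTcF increase must be confirmed as lasting at least 5 minutes on a repeat ECG. A scheduled triplicate is captured within a 5-minute window, so one triplicate cannot by itself show this.
- The pulse and blood-pressure limits require persistence for at least 10 minutes. The limit of 45 bpm also requires symptoms, and both low-pulse limits apply only to waking subjects. The schedules contain no dedicated 10-minute repeat of vital signs.
- Scheduled ECGs end at Day 43 (Cohorts 1-3) or Day 38 (Cohort 4) according to Tables 4.2-1 and 4.2-2. Vital signs continue to Day 71 or Day 66.

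A count from scheduled values is therefore feasible, but it is a looser quantity than the pause criteria, and its ECG part ends earlier than the endpoint period.

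**The case against.** The strongest reply is that individual events are not lost.

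- **Listings.** SAP 3.1 plans listings by cohort, treatment group and subject number. With six active subjects per cohort, a reader can tell case A from case B there.
- **Adverse events.** Protocol 5.1 has ECG findings reported as AEs when they need intervention or are judged medically significant, and protocol 4.3.1.4 adds notification by the central reader. SAP 3.5.1 counts each specific AE once per subject.
- **Table specifications.** SAP section 1 places these in a separate statistical programming plan that is not public. The ECG sentence in 3.5.5.2 is also loose enough to admit a categorical parameter.
- **Escalation review.** The two-subject level is a matter for the Dose Escalation Committee, which receives its own ECG and vital-sign listings.

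These points stand in part. They rule out two stronger readings. A reader might infer that the number of affected subjects will never be available. The documents do not support that: listings and TEAE tables give partial information, and the programming plan is unseen. A reader might also infer that protocol 3.1.3 already defines clinical importance for the endpoint. It does not; it sets pause criteria, and neither document links them to the endpoint wording.

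The gap remains all the same. A hand count from listings with no stated limit is post hoc. The AE route depends on investigator judgement, is less explicit for vital signs, and records the diagnosis instead of the finding when there are clinical sequelae. The endpoint also names these changes in addition to TEAEs, so TEAE counts alone leave that component without its own analysis. A descriptive phase 2a approach to safety is reasonable, and a count with a percentage fits within it.

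**Conclusion.** The point holds as a mismatch between the endpoint and its specified analysis. For ECG and vital signs the SAP states only group summaries by time point, which cannot show how many different subjects had a marked change. In the illustration the same rows fit 1/6 and 2/6 subjects, a difference of 16.7 percentage points in an active group. That size rests on assumed QTcF values and on the planned group size of 6. The conclusion that the count is not determined needs no particular value, because the summaries do not link subjects across visits. It applies to what the SAP specifies; the unseen programming plan may contain more. The matter should be corrected before analysis, but it does not threaten data collection or the conduct of the study.

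**What to change.** In SAP 3.5.5.1 and 3.5.5.2 add, by treatment group with placebo combined, the number and percentage of subjects with at least one scheduled post-baseline value beyond a pre-stated numeric limit:

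- **ECG:** triplicate-mean QTcF, with separate rows for an absolute value above 500 ms and an increase from baseline above 60 ms, through the last scheduled ECG (Day 43 for Cohorts 1-3, Day 38 for Cohort 4).
- **Vital signs:** the numeric values in protocol 3.1.3, namely pulse above 125 bpm, below 45 bpm and below 30 bpm, and a systolic rise of more than 40 mm Hg to above 180 mm Hg, through Day 71 or Day 66.

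Label these as analysis categories based on single scheduled readings. State that they are not the confirmed or persistent pause criteria of protocol 3.1.3 and that they change no decision rule. Keep the existing descriptive tables.

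The cost is two short SAP additions and two tables from readings already scheduled. The drawback is that an isolated, unconfirmed crossing will be counted, and the label tells the reader so.
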